9.4.2 Biomarkers

Biomarkers including fasting insulin, adiponectin, low- and high-density lipoproteins, cholesterol, and triglycerides will be listed and summarized by Part, treatment and timepoint.

Untransformed absolute values as well as change from baseline in each parameter will be analyzed, separately for each Part, using a mixed-model repeated-measure model to evaluate treatment effects as well as treatment comparisons. The model will include treatment, timepoint and treatment-by-day interaction as fixed effects, subject as a random effect and baseline as a covariate (for the change from baseline analysis). An unstructured covariance structure will be used and a compound symmetric structure will be used if the model fails to converge. The analysis will compare each dose of LY3478045 against placebo at each day. Least squares means as well as 90% CIs will be reported.

Example of SAS code as follows.

```
proc mixed data=xxxx;
class treatment timepoint subject;
model result = treatment timepoint treatment*timepoint /residual ddfm=kr;
repeated timepoint / subject=subject type=UN;
lsmeans treatment*timepoint / cl pdiff alpha=0.1;
ods output lsmeans=lsm diffs=estims;
run;
```

The above code will include baseline as a covariate for the change from baseline parameters.

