9.4.3 Fructose Tolerance Test

Fructose Tolerance Test (FTT): Three meals (breakfast, lunch, and dinner) will be served at approximately 20 minutes, 6 hours, and 12 hours after dose with low fructose content. A beverage containing mixture of fructose CCI CCI in approximately 300 to 500 mL of non-caloric solution) will be served with each of the

3 meals on Day 1 in Part A, and Days 1 and 14 in Part B. AUC(0-24), AUC(0-6), AUC(6-12), and AUC(12-24) for FTT will be calculated using trapezoid methods.

In Part A, the AUC(0-24), AUC(0-6), AUC(6-12), and AUC(12-24) from the FTT will be log-transformed prior to analysis. A linear fixed effects model will be fitted to the fructose data. The model will include Treatment as a fixed effect. The difference in least-square treatment means (LY3478045 – Placebo) along with the 90% CIs will be back-transformed to produce the ratio of geometric means and the CIs comparing LY3478045 to Placebo.

Example of SAS code as follows:

```
proc mixed data=xxx;
class treatment;
model log_AUC = treatment /residual ddfm=kr;
lsmeans treatment / cl pdiff alpha=0.1;
ods output lsmeans=lsm diff=estims;
run;
```

In Part B, the AUC(0-24), AUC(0-6), AUC(6-12), and AUC(12-24) from the FTT will be log-transformed prior to analysis. A linear mixed effects model will be fitted to the data. The model will include treatment, day and the interaction between treatment and day as fixed effects and subject as a random effect. The difference in least-square treatment means (LY3478045 – Placebo) along with the 90% CIs will be back-transformed to produce the ratio of geometric means and the CIs comparing LY3478045 to Placebo. Similar comparisons will be calculated between Day 14 and Day 1 for LY3478045.

Example of SAS code as follows:

```
proc mixed data=xxx;
class treatment day subject;
model log_AUC = treatment|day /residual ddfm=kr;
random subject;
lsmeans treatment*day / cl pdiff alpha=0.1;
ods output lsmeans=lsm diff=estims;
run;
```

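### SAP 9.4.2 plans two untransformed inferential analyses of the same biomarker effect, one without baseline, and does not say which leads

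*SAP*

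**What the plan says.** SAP 9.4.2 covers six analytes: "Biomarkers including fasting insulin, adiponectin, low- and high-density lipoproteins, cholesterol, and triglycerides will be listed and summarized by Part, treatment and timepoint". The modelling sentence is: "Untransformed absolute values as well as change from baseline in each parameter will be analyzed, separately for each Part, using a mixed-model repeated-measure model". The fixed effects are treatment, timepoint and their interaction, with "baseline as a covariate (for the change from baseline analysis").

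The example code agrees. Its model line is "model result = treatment timepoint treatment*timepoint /residual ddfm=kr", with no baseline term, and the note beneath it reads: "The above code will include baseline as a covariate for the change from baseline parameters".

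Both versions are inferential: "The analysis will compare each dose of LY3478045 against placebo at each day", and "Least squares means as well as 90% CIs will be reported". Protocol 10.3.3.2 adds unadjusted p-values. Nothing ranks the two versions.

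Elsewhere the SAP works on the log scale. In 9.4.3 the fructose AUCs "from the FTT will be log-transformed prior to analysis". In 9.3.1 the Day 7 to Day -2 comparison uses the logged ratio as response, with log baseline as a fixed effect.

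**The concern.** Two models that target the same dose-versus-placebo difference, with no stated order between them, leave the reader of the study report to choose. If one interval excludes zero and the other does not, the SAP gives no basis for preferring either. The version without baseline carries the full between-subject spread, in a population admitted with a BMI from 18.5 to 40 (Protocol 6.1) and with 6 subjects per dose.

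A second, weaker question is the scale. Section 9.4.2 fixes an additive effect on raw concentrations, although the SAP logs its PK parameters and fructose AUCs, and it gives no reason for the difference.

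**Working it through.** The documents give no SD, correlation, effect size or power for these biomarkers (Protocol 10.1 and SAP 7 state none), so there is no planned figure to reproduce.

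**Inputs from the documents**
- Sampling (Protocol 2.2 and 2.3): fasting insulin and adiponectin are drawn predose on Day 1 and Day 14. They are not in the Part A schedule (2.1). Each subject has one baseline and one post-baseline value.
- Allocation (SAP 5.2): 6 active and 2 placebo per Part B cohort, up to 4 cohorts. That gives 6 per dose and 4 × 2 = 8 placebo if pooled. SAP 6 lists two Part B placebo treatments, so 2 × 2 = 4 each if not pooled. Section 9.4.2 does not say which applies.
- 90% intervals, which correspond to a two-sided 10% test.

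**Assumed, not in the documents:** the baseline to Day 14 correlation ρ, lognormal data, the CVs, and a 40% fall or rise.

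**1. Both models estimate one effect.** Write Y for Day 14, B for baseline and T for treatment. The change model is Y − B = a + τT + bB. Rearranged, Y = a + τT + (b + 1)B. Adding baseline to the absolute-value model therefore returns the same τ and the same interval. The only difference between the planned analyses is whether baseline is in the model.

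**2. The absolute-value contrast is unadjusted.** With complete data, the treatment-by-timepoint least-squares means are the raw cell means under either planned covariance structure (unstructured or compound symmetric). The Day 14 contrast is then a plain difference of group means.

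**3. Size of the penalty.** Ratio of unadjusted to adjusted standard error = 1/√(1 − ρ²); equivalent sample-size multiplier = 1/(1 − ρ²).

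| ρ | SE ratio | Sample-size multiplier |
|---|---|---|
| 0.3 | 1.05 | 1.10 |
| 0.5 | 1.15 | 1.33 |
| 0.7 | 1.40 | 1.96 |
| 0.8 | 1.67 | 2.78 |
| 0.9 | 2.29 | 5.26 |

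The formula is slightly generous at this size. In lognormal simulation with 8 placebo, CV 70% and no effect, the ratio was 0.427/0.317 = 1.35 at ρ = 0.7 and 0.420/0.196 = 2.14 at ρ = 0.9.

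**4. In power terms**, for an assumed effect of 1 SD, 6 versus 8: 58% unadjusted, against 69%, 83%, 93% and 99.5% adjusted at ρ = 0.5, 0.7, 0.8 and 0.9. For 6 versus 4: 46%, against 56%, 70%, 83% and 97%.

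**5. Scale.** Simulated power, lognormal data, 6 versus 8, two-sided 10%. The log model uses log(Day 14/baseline) with log baseline as covariate.

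| CV between / within | 40% fall: raw absolute | 40% fall: raw change, adjusted | 40% fall: log ratio, adjusted | 40% rise: raw change, adjusted | 40% rise: log ratio, adjusted |
|---|---|---|---|---|---|
| 40% / 25% | 0.56 | 0.77 | 0.83 | 0.52 | 0.54 |
| 60% / 25% | 0.36 | 0.70 | 0.81 | 0.47 | 0.52 |
| 60% / 35% | 0.32 | 0.49 | 0.60 | 0.32 | 0.35 |
| 80% / 35% | 0.23 | 0.44 | 0.59 | 0.28 | 0.34 |

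For a fall, the log model gains 0.06, 0.11, 0.11 and 0.15 over the planned adjusted model. For a rise it gains 0.02, 0.05, 0.03 and 0.06, and repeat runs put the smallest gain nearer 1 point. At other CVs and correlations the difference for a rise was sometimes reversed: at CV 70% and ρ = 0.5, power was 0.31 raw and 0.28 log.

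**6. Disagreement.** In these four scenarios with a 40% fall, the two planned raw analyses reached opposite significance conclusions in about 30 to 47% of simulated trials. Under no effect, each test alone stayed near 10%, but at least one of the two was significant in about 14 to 16%.

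**The case against.** The strongest reply is that the efficient analysis is already in the plan. Change from baseline with baseline as covariate is an analysis of covariance when there is one post-baseline value. A reader might infer that the trial gives up the power of baseline adjustment; it does not. The low powers in the raw-absolute column belong only to the duplicate model. This stands.

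A reader might also infer that the raw scale costs power for insulin and adiponectin alike. The documents do not support that. They give no distribution for either analyte, and simulating lognormal data with a multiplicative effect makes the log model correct by construction. Protocol 3.2.2 cites a decrease for insulin but an increase for adiponectin, and for an increase the gain is small or absent. The cited effects also come from patients with NAFLD treated for 6 weeks, so a 40% change after 14 days in healthy subjects is only illustrative. All of this stands.

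The four CV pairs imply log-scale correlations of about 0.71 to 0.84, where an unadjusted contrast looks poor; at 0.5 the penalty is only 15%. That also stands, so the size has to be given as a range.

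Finally, absolute values have a use: they show means in natural units and, if Day 1 is included as a timepoint, within-treatment differences. That supports displaying them. It does not support a second between-treatment test of unstated rank.

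**Conclusion.** The point holds as a redundancy without a stated order. SAP 9.4.2 plans two untransformed inferential estimates of one effect, leaves one of them unadjusted for baseline, and names neither as leading. That much follows from the text and the algebra alone.

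The size depends on an assumed correlation: a standard error about 1.15 to 2.3 times larger over ρ = 0.5 to 0.9, confined to the absolute-value model. The case for the log scale is conditional on right-skewed data. It is material for a fall (about 6 to 15 points) and slight for a rise (about 1 to 6). The figures for 6 versus 8 assume that the two Part B placebo groups are pooled.

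The simulations do not suggest that either test is invalid, since each keeps its error rate near nominal. Importance is limited: the fructose tolerance test is the primary PD measure (Protocol 10.3.3.1), these biomarkers are exploratory, and no power is claimed for them. This is a worthwhile tidy-up, not a necessary correction.

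**What to change.** In SAP 9.4.2:

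- Make the baseline-adjusted model the only inferential analysis for all listed biomarkers, lipids included. Present absolute values as descriptive summaries; within-treatment means in natural units can still be shown.
- For insulin, and for consistency adiponectin, take log(Day 14/baseline) as the response with log baseline as covariate, as SAP 9.3.1 already does for its Day 7 to Day -2 ratio. Report LY3478045-to-placebo geometric mean ratios with 90% CIs. If the raw scale is kept, give the reason.
- State whether the two Part B placebo groups are pooled for this analysis.

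The cost is SAP wording and a small change to the example code, with no change to data collection. The downside is that insulin and adiponectin effects are reported as ratios instead of concentration units; the descriptive tables keep the units available.

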9.4.3 Fructose Tolerance Test

Fructose Tolerance Test (FTT): Three meals (breakfast, lunch, and dinner) will be served at approximately 20 minutes, 6 hours, and 12 hours after dose with low fructose content. A beverage containing mixture of fructose CCI CCI in approximately 300 to 500 mL of non-caloric solution) will be served with each of the

3 meals on Day 1 in Part A, and Days 1 and 14 in Part B. AUC(0-24), AUC(0-6), AUC(6-12), and AUC(12-24) for FTT will be calculated using trapezoid methods.

In Part A, the AUC(0-24), AUC(0-6), AUC(6-12), and AUC(12-24) from the FTT will be log-transformed prior to analysis. A linear fixed effects model will be fitted to the fructose data. The model will include Treatment as a fixed effect. The difference in least-square treatment means (LY3478045 – Placebo) along with the 90% CIs will be back-transformed to produce the ratio of geometric means and the CIs comparing LY3478045 to Placebo.

Example of SAS code as follows:

```
proc mixed data=xxx;
class treatment;
model log_AUC = treatment /residual ddfm=kr;
lsmeans treatment / cl pdiff alpha=0.1;
ods output lsmeans=lsm diff=estims;
run;
```

In Part B, the AUC(0-24), AUC(0-6), AUC(6-12), and AUC(12-24) from the FTT will be log-transformed prior to analysis. A linear mixed effects model will be fitted to the data. The model will include treatment, day and the interaction between treatment and day as fixed effects and subject as a random effect. The difference in least-square treatment means (LY3478045 – Placebo) along with the 90% CIs will be back-transformed to produce the ratio of geometric means and the CIs comparing LY3478045 to Placebo. Similar comparisons will be calculated between Day 14 and Day 1 for LY3478045.

Example of SAS code as follows:

```
proc mixed data=xxx;
class treatment day subject;
model log_AUC = treatment|day /residual ddfm=kr;
random subject;
lsmeans treatment*day / cl pdiff alpha=0.1;
ods output lsmeans=lsm diff=estims;
run;
```

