7.1. Treatment Administered

LY3478045 or placebo will be administered orally with approximately 240 mL of room temperature water in the morning of each dosing day (Day 1 in SAD; Days 1 to 14 in MAD) in a sitting position. Subjects will not be allowed to lie supine for 2 hours after dosing, unless clinically indicated or for study procedures.

Table GZKA.3. Treatments Administered

Treatment Name	LY3478045	Placebo	Atorvastatin
Dosage Formulation	CC1	Capsules	Tablets
Dose strength		-	40 mg
Route of Administration	Oral	Oral	Oral

The investigator or designee is responsible for

- explaining the correct use of the investigational product(s) to the site personnel
- verifying that instructions are followed properly
- maintaining accurate records of investigational product dispensing and collection, and
- returning all unused medications to Lilly or its designee at the end of the study

Note: In some cases, sites may destroy the material if, during the investigative site selection, the evaluator has verified and documented that the site has appropriate facilities and written procedures to dispose off the clinical materials.

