5.2 Part B

[figure not shown]
Part B will be initiated after assessing safety, tolerability, PK, and PD data through Cohort 3 in Part A.

Multiple-ascending oral doses of LY3478045 will be administered once daily (QD) for 14 days in up to 4 cohorts. Each cohort will consist of 8 subjects. In Cohorts 1 and 3, six subjects will receive LY3478045 and 2 subjects will receive placebo. In Cohorts 2 and 4, six subjects will receive LY3478045 co-administered with a single dose of [CC1] and 2 subjects will receive placebo with a single dose of [CC1]. The maximum dose in males and females will be determined based on the PK analyses from previous cohorts.

A sentinel dosing strategy will be utilized in Cohorts 3 and 4, for which the mean AUC(0-24) is predicted to exceed [CC1] $\mu\text{g}\cdot\text{hr}/\text{mL}$. Two subjects (1 LY3478045 and 1 placebo) in the cohorts for which the mean AUC0-24 is predicted to exceed [CC1] $\mu\text{g}\cdot\text{hr}/\text{mL}$ will receive a sentinel dose on the same day. At least 48 hours after dose, the remaining subjects in each cohort may be dosed based on the available safety data.

Male subjects are allowed in Part B in the cohorts for which the predicted mean exposure AUC0-24 levels for the dose will not exceed [CC1] $\mu\text{g}\cdot\text{hr}/\text{mL}$, 1/10th exposure level observed at [CC1] mg/kg in dogs, which is the lowest dose tested in dogs with no testicular findings, as determined from PK data in Parts A and B.

Female subjects are allowed in Part B in every cohort. The predicted mean exposure AUC0-24 levels for the doses investigated in Part B will not exceed [CC1] $\mu\text{g}\cdot\text{hr}/\text{mL}$, 1/12th exposure level observed at [CC1] mg/kg in dogs, as determined from PK data in Parts A and B.

Abbreviations: AT = atorvastatin; LY = LY3478045; PL = placebo.

Figure GZKA.2 Illustration of study design for Part B

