8. DEFINITION OF ANALYSIS POPULATIONS

The “Safety” population will consist of all enrolled subjects, whether they completed all protocol requirements.

The “Pharmacokinetic” population will consist of all subjects who received at least one dose of study drug and have evaluable PK data. If a subject has an AE of vomiting that occurs before 2 times the median t_{max} after dosing, then that subject may be excluded from the PK summary statistics and statistical analysis.

The “Pharmacodynamic” population will consist of all subjects who received at least one dose of study drug or placebo and have evaluable PD data.

All protocol deviations that occur during the study will be considered for their severity/impact and will be taken into consideration when subjects are assigned to analysis populations.

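### SAP 9.4.3 plans the Day 14 versus Day 1 fructose comparison within LY3478045 only; the placebo-adjusted change, available from the same model, is not specified

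*SAP*

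**What the plan says.** SAP 9.4.3 sets out one Part B model for the log of each fructose AUC: "The model will include treatment, day and the interaction between treatment and day as fixed effects and subject as a random effect". The first planned result compares arms: "The difference in least-square treatment means (LY3478045 – Placebo) along with the 90% CIs will be back-transformed". The next sentence turns to time: "Similar comparisons will be calculated between Day 14 and Day 1 for LY3478045". Placebo is not named there, and no difference of changes is defined.

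The example code requests "lsmeans treatment*day / cl pdiff alpha=0.1". This gives every pairwise difference between treatment-by-day cells, with 90% CIs. It has no statement for the interaction contrast.

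Placebo subjects are in this analysis. The SAP section 8 PD population is "all subjects who received at least one dose of study drug or placebo and have evaluable PD data", and the fructose beverage is served with "3 meals on Day 1 in Part A, and Days 1 and 14 in Part B". Protocol 7.1 gives the dosing days as "Day 1 in SAD; Days 1 to 14 in MAD", so Day 1 is already an on-drug day for LY subjects.

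**The concern.** On the log scale, the LY Day 14 minus Day 1 difference is the sum of two things: the change in drug effect, and whatever changed between the two test days for everyone. Subjects are admitted on Day -1 (Cohorts 1 and 3) or Day -3 (Cohorts 2 and 4) and discharged on Day 17, so there is a long residential stay. Cohorts 2 and 4 also take atorvastatin on Day 7, between the tests. Placebo subjects follow the same schedule and are the control for these influences, but the Day 14 versus Day 1 comparison does not use them.

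What is at stake is one question: does the PD effect build or fade over 14 days of dosing? A ratio shown for LY3478045 alone invites that reading, and it cannot support it.

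Other parts of the SAP do bring placebo into change over time. SAP 9.3.1 models the log ratio of Day 7 to Day -2 for the co-administered drug and compares LY3478045 with placebo. SAP 9.4.1 plans its postdose versus predose comparison for placebo as well as for each dose.

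**Working it through.** The documents state no figure for this contrast, so there is none to reproduce.

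**Inputs from the documents.** "In Cohorts 1 and 3, six subjects will receive LY3478045 and 2 subjects will receive placebo" (SAP 5.2). Cohorts 2 and 4 have the same 6:2 split. Up to 4 cohorts gives 4 x 6 = 24 LY subjects in four treatment groups and 4 x 2 = 8 placebo subjects, 32 in all. This matches the 32 completers in SAP section 7. SAP section 6 lists two Part B placebo treatments, so placebo is 8 if pooled or 4 + 4 if kept apart. The CI level is 90%.

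**Assumptions.** Within-subject log SD (sw) of 0.15 to 0.40, a multiplicative shift s of 1.10 or 1.20 shared by both arms, a drug effect that does not change, and complete pairs.

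**Formulas, per dose.**
- Within-LY contrast: SE = sw x sqrt(2/6). Its expectation is ln(s), where a constant drug effect should give 0.
- Placebo-adjusted contrast: SE = sw x sqrt(2/6 + 2/nP). Its expectation is 0, because ln(s) cancels.
- Degrees of freedom: 32 - 5 = 27 with pooled placebo, 32 - 6 = 26 with split placebo.
- Coverage of a ratio of 1 by the within-LY CI: P(|T| < t0.95,df), where T is noncentral t with noncentrality ln(s)/SE. For 27 df, t0.95 = 1.703.

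**Example.** With sw = 0.20, SE = 0.20 x 0.577 = 0.1155. For s = 1.20, noncentrality = 0.1823/0.1155 = 1.58 and coverage is 54%.

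| sw (assumed) | SE, within LY | Coverage, s = 1.10 | Coverage, s = 1.20 |
|---|---|---|---|
| 0.15 | 0.087 | 71% | 34% |
| 0.20 | 0.115 | 79% | 54% |
| 0.30 | 0.173 | 85% | 73% |
| 0.40 | 0.231 | 87% | 80% |

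With 26 df the results are the same to the nearest percentage point.

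**Simulation check.** In 20,000 runs with s = 1.20, within-subject CV 20% (log SD 0.198), pooled placebo and no drug-specific change, the within-LY ratio averaged 1.20 and its 90% CI excluded 1 in 46% of runs. The placebo-adjusted ratio averaged 1.00 and its CI excluded 1 in 10.3% (nominal 10%).

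**Price in precision.** The SE ratio is sqrt((1/6 + 1/8)/(1/6)) = 1.32 with 8 pooled placebo subjects and sqrt((1/6 + 1/4)/(1/6)) = 1.58 with 4. At sw = 0.20 the 90% CI multiplies and divides the ratio by:
- within LY: exp(1.703 x 0.1155) = 1.22
- adjusted, pooled placebo: exp(1.703 x 0.20 x sqrt(2/6 + 2/8)) = 1.30
- adjusted, split placebo: exp(1.706 x 0.20 x sqrt(2/6 + 2/4)) = 1.37

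**The case against.** Several stronger readings are tempting, and the documents do not support them.

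- *A reader might infer that the SAP counts a period shift as a drug effect.* It does not call the Day 14/Day 1 ratio a drug effect. Its drug effect is LY3478045 minus placebo. A common shift cancels from that difference on Day 1, on Day 14, and if averaged over both days.
- *A reader might infer that the study has no drug-free fructose test.* Placebo subjects have one on both days, and the fix depends on those tests. What is missing is a pre-dose test in LY subjects.
- *A reader might infer that two weeks of repeated fructose loading must move the result.* The Part B schedules list the beverage only on Days 1 and 14, with the same meal times on both. No document supports a shift of 10% or 20%; these are illustrations.

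It can also be said that little is missing. The pairwise output already contains the placebo Day 14 minus Day 1 difference with a CI, and LY minus placebo on each day. Subtracting gives the point estimate of the adjusted change, the procedure prints an overall interaction test by default, and SAP section 3 allows supplementary analyses. This stands, and it makes the gap an unspecified contrast rather than missing data. But the reader would get no CI for the drug-specific change at each dose, and the only change over time that the text names is the unadjusted one.

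The impact is limited too. Protocol Table GZKA.1 lists the PD objective as exploratory, with no stated aim about the effect building or fading. Protocol 7.4 makes safety and tolerability the primary escalation criteria, and Protocol 5.5 assigns target engagement to Part A. No stated decision rests on this ratio.

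**Conclusion.** The point holds in a limited form. The planned within-LY ratio estimates the drug-specific change multiplied by any shift shared with placebo; that follows from the contrast itself and needs no assumed SD. The cost in coverage does need assumptions. Across log SDs of 0.15 to 0.40, nominal 90% coverage falls to between 71% and 87% for a 10% shift and to between 34% and 80% for a 20% shift. The loss is mild if fructose AUC is highly variable or the shift is small, and nil if there is no shift. The Day 1 and Day 14 comparisons with placebo stand as planned. For an exploratory endpoint this is a cheap improvement, not a flaw in the main PD result.

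**What to change.** In SAP 9.4.3, for each Part B dose, add the treatment-by-day contrast (LY Day 14 - Day 1) minus (placebo Day 14 - Day 1), back-transformed to a ratio with a 90% CI. In the existing model this is one ESTIMATE statement per dose: coefficients +1 and -1 on the LY Day 14 and Day 1 cells, -1 and +1 on the placebo cells, and zero on the main effects. Base any statement about drug-related change over time on this contrast. Report the within-LY and within-placebo Day 14/Day 1 ratios beside it.

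State whether the two Part B placebo groups are pooled for this model. Pooling gives 8 comparators but assumes that the Day 1 to Day 14 shift is the same with and without the co-administered drug. Keeping them apart leaves 4.

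No new data, visits or model are needed. The cost is a wider interval: SE 1.32 times that of the within-LY contrast if pooled, 1.58 times if split.
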